Shingo Kuroda et al. (2007), Evaluated the clinical usefulness of mini-implants as orthodontic anchorage. examined their success rates, analyzed factors associated with their stability, and evaluated patients' postoperative pain and discomfort with a retrospective questionnaire. Seventy-five patients, 116 titanium screws of 2 types, and 38 miniplates were retrospectively examined. The success rate for each type of implant was greater than 80%. He concluded that miniscrews placed without flap surgery have high success rates with less pain and discomfort after surgery than miniscrews placed with flap surgery or miniplates placed with either procedure⁴⁰.

Database research:

A search was performed on electronic databases (PubMed, Cochrane library).

III- Aim of the study

The aim of this study is to evaluate the Effect of Bilateral Distalization of Upper First Molars in a Group of Patients after extraction of Maxillary Second Molars Using Infra Zygomatic Mini Implants.

A-PICO format :

Patient/Population :

Adult patients having Class II molar relation. And indicated for maxillary molar distalization.

Intervention:

Infra-zygomatic mini implant supported maxillary intra oral appliance & extraction of maxillary second molars.

Comparator:

Pre-treatment and post treatment maxillary and mandibular changes.

Out-come mesure(s):

Prioritization of the outcome	outcome	Method of measurement	Unit of measurement
primary	Anteroposterior Dental changes in the upper buccal segment	Scanned dental cast e.g. (MB cusp of U6-MB groove of L6) CBCT	Millimeters
secondary	other dental changes in upper buccal segment including (intermolar width, molar inclination,)	Scanned dental cast CBCT	Millimeters and degrees
	dental changes in mandibular teeth.	Scanned dental cast	Millimeters

B-Research question :

Will the proposed appliance be able to induce dental effects for correction of class II malocclusion in adult patients after extraction of upper second molars within the duration of eight months?

IV-Objectives of the study

•Research hypothesis:

The null hypothesis of this research is that there are no dental changes associated with the use of proposed appliance.

•Primary objective (s):

Amount and rate of maxillary 1st molar Distalization.

•Secondary objective:

Evaluate the other dental changes in the upper buccal segment accompanying the Distalization technique and the consequent dental changes in the mandibular arch.

•Study design

Prospective clinical trial.

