Orthodontic force 350 mg per side Will be delivered by Niti closed coil spring which is attached from infra zygomatic mini screw to the hook soldered to the wire framework.

Patient will wear mandibular thermoform retainer at night only.

E-Follow up period:

The patient will be asked to attend follow up visits every 4 weeks to check the following:

- A) The stability of the mini implants
- B) The activity of the appliance (force recalibration is required).
- C) The amount of correction achieved.
- D) Any inflammation related to the appliance or the mini implants

Impressions and wax bite will be taken (without the appliance in place) followed by digital scanning of produced models).

F-Criteria for discontinuing intervention:

Any harmful effects to the patient from any of the treatment modalities

Lack of patient co-operation

Outcomes:

Primary: Anteroposterior position changes of upper first molars.

Secondary: Other dental changes in upper post segment and mandibular dental arch.

Methods of measuring of all outcomes:

Linear and angular measurements Will be made on the pre, post and follow-up dental scanned casts and on the CBCT to assess the dental changes in intervention group.

Units of measurement:

Millimetres and degrees

Blinding:

- Due to the nature of the study, the operator and patients can't be blinded. Blinding of the outcome assessors can be done by sealing the name of the patient in the pre and post treatment radiographs used for analysis.

VI- Sample size

Our sample size calculation is based on a previous study³¹ evaluating the dentoalveolar, skeletal, and soft tissue effects of the Zygoma-Gear Appliance (ZGA) when used for bilateral distalization of the maxillary molars. as the Primary outcome values was:

[figure not shown]
	Before	After	Difference
VRL-U6	32.05 ± 4.01	27.66 ± 4.17	-4.36 ± 2.15

The plan of the study is a continuous response variable from matched pairs of study subjects. Prior data indicate that the difference in the response of matched pairs is normally distributed with standard deviation 2.15. If the true difference in the mean response of matched pairs is 4.36, we will need to study 5 pairs of subjects to be able to reject the null hypothesis that this response difference is zero with probability (power) 0.8. The Type I error probability associated with this test of this null hypothesis is 0.05. So, to count for drop out or missing data a sample of size of 8 pairs of subjects is recommended

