Type of test: Paired t Test

Minitab software output.

Sample	Target		
Difference	Size	Power	Actual Power
4.36	5	0.8	0.915696

To count for drop out or missing data a sample of size 8 is recommended

VII-Data collection, management and analysis:

Patients recruited from the clinic at the department of orthodontics at Future university in Egypt

The data collection for the primary and secondary outcomes will be done by taking scanned dental casts and CBCT.

Pre and post treatment/ observation period in the treatment

Plans to promote participants retention and complete follow-up:

- Telephone numbers of all patients included in the study will be recorded as a part of the written consent.
- All patients will be given reminder phone calls at the time of the predetermined follow updates.
- Patient punctuality at appointments, number of missed appointments will be regularly monitored.

- **Data management:**
- All data will be electronically entered in the computer at the Department of Orthodontics and Dentofacial Orthopedics. The data should include all photographs, models and radiographs.
- Resulted data from scanned cast analysis will be organized in excel sheets that will be electronically entered and backed up in a google drive for permanent storage.
- The patients' data should have sequential numbers that will be revised at each step to avoid any mixing of data between patients.

Statistical analysis:

The principle investigator will be responsible for the extraction of the required data from the CBCT taken before and after retraction as well as the study models taken at every follow up visit. The data will be sent to a specialized statistician.

VIII-Monitoring:

A) Data monitoring:

Monitoring of the study will be strictly done by the supervisors periodically. They will monitor all the steps of the followed protocol and find solutions to all troubles that have occurred during the trial performance.

B) Harms:

If any harm occurs to the patient before entry to the study, it will be reported as unrelated. If it happens after, it will be recorded and documented by the primary investigator. Severity of harms and potential causal relationship with intervention will be addressed. In cases of inflammation of the tissue around the mini-implant, immediate removal of the mini-implant and prescription of anti-inflammatory drugs will be done in order to subside the inflammation followed by replacement of the mini-implant after the resolution of the inflammation.

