C) Auditing:

The supervisor will follow up and review the different interventions and resulting data. And he will periodically follow up the trial progress including recruitment of patients, adherence to interventions and reporting of harms. A meeting with the senior supervisor will be set to monitor the progress of the study and the need for any adjustments.

Research ethics approval:

This protocol and the template informed consent form will be reviewed by the Ethics Committee of Scientific Research –Faculty of Oral and Dental Medicine- Future University in Egypt.)

Protocol amendments:

Any modification to the protocol which may have an impact on the conduct of the study, potential benefit of the patient or may affect patient safety will require a formal amendment to the protocol. Such amendment will be agreed upon by the Department of Orthodontics and Dentofacial Orthopedics, Faculty of Oral and Dental Medicine, Future University in Egypt and the Ethics Committee will approve such amendment before proceeding in the study.

Consent:

The main investigator will be in charge for detailed explanation and elaboration of the different steps of the study interventions for each patient. Then will ask every participant to sign a written consent before they begin treatment. The consent will be written in Arabic.

Confidentiality:

The main investigator will store any personal information about the participants collected during the study separately from study records in locked files in areas with only access to the supervisors responsible for auditing and analysis. Also, will keep the files in the Department of Orthodontics and Dentofacial Orthopedics, Faculty of Oral and Dental Medicine, Future University in Egypt and will identify all the reports, data and administrative forms by a coded ID number to maintain participant confidentiality. Participant information won't be used outside the study except with written permission of the participant.

Declaration of interests:

No financial interests are to be declared by the supervisors and the principle operator. This study is a part of a Masters' degree in Orthodontics, Faculty of Oral and Dental Medicine, Future University in Egypt and it is self-funded by the principal investigator.

Ancillary and Post Trial Care:

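### Assessor blinding hides the patient's name on radiographs, but not the time point, which is the only thing this one-group study compares

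*Protocol*

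**What the plan says.** The PICO table in section III (Aim of the study) gives the comparator as "Pre-treatment and post treatment maxillary and mandibular changes". There is one intervention group, and section VI plans a paired t test. The primary objective in section IV is "Amount and rate of maxillary 1st molar Distalization".

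The Blinding paragraph in section V says that operator and patients cannot be blinded. On assessors it says: "Blinding of the outcome assessors can be done by sealing the name of the patient in the pre and post treatment radiographs".

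The records to be measured are wider than radiographs. Under the methods of measuring outcomes in section V: "Linear and angular measurements Will be made on the pre, post and follow-up dental scanned casts and on the CBCT". The PICO table lists both scanned casts and CBCT for the primary outcome, and scanned casts alone for the mandibular changes.

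The Statistical analysis paragraph in section VII says who handles the measurements: "The principle investigator will be responsible for the extraction of the required data from the CBCT taken before and after retraction". The same duty extends to the casts, which that sentence brings in with the words "as well as the study models taken at every follow up visit".

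Two other passages mention coding. Under Data management, patients' data "should have sequential numbers that will be revised at each step to avoid any mixing of data between patients". Under Confidentiality, the investigator "will identify all the reports, data and administrative forms by a coded ID number to maintain participant confidentiality".

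**The concern.** In a parallel-group trial, a reader who does not know the treatment arm cannot favour one arm. This trial has no second arm, so the corresponding information is the time point of the record. A reader who knows that an image is post-treatment may place a landmark slightly further distally. Concealing the name does nothing about that.

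There are two further gaps. The sentence covers radiographs only, although casts are a primary-outcome source and the only record taken at every follow-up visit. Any rate estimated between visits would therefore rest on records for which no masking is stated. In addition, the Blinding paragraph speaks of outcome assessors, while section VII makes the principal investigator responsible for extracting the data, so the reader's identity is open.

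At stake is the size of the estimates. With no control group to subtract it, a reading bias that depends on time point passes in full into the amount and rate of distalization. It also passes into smaller secondary changes such as intermolar width and mandibular movement.

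**Working it through.** **Step 1: what each provision conceals**

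| Provision | Records covered | Stated purpose | Conceals time point? |
|---|---|---|---|
| Blinding paragraph (V) | Pre and post radiographs | Blinding, by sealing the name | No |
| Sequential numbers (VII, Data management) | Patients' data | Avoiding mix-ups | Not stated |
| Coded ID (Confidentiality) | Reports, data, forms | Confidentiality | Not stated |

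No provision is said to hide the visit, and none sets a random reading order.

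**Step 2: the plan's own figure**

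Inputs from section VI: mean paired difference 4.36 mm, SD 2.15 mm, Type I error 0.05, paired t test. Sidedness is not stated; two-sided is used because it reproduces the output. The noncentrality is (4.36 / 2.15) × √n.

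- n = 4: power 0.765
- n = 5: noncentrality 4.535, critical t (4 df) 2.776, power 0.9157, matching the stated 0.915696
- n = 8: noncentrality 5.736, critical t (7 df) 2.365, power 0.9980

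**Step 3: effect of a reading bias**

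The documents give no reading error. Assume that an unmasked reader adds b = 0.25, 0.5 or 1.0 mm to the mean change. A constant error that is the same at both time points would cancel; b is only the part that differs between them. The SD of 2.15 mm is taken from section VI, where it belongs to VRL-U6 in a previous study. Applying it to other measures is a further assumption.

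Half-width of the 95% interval = t × 2.15 / √n:

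- n = 8: 2.365 × 0.760 = 1.80 mm
- n = 5: 2.776 × 0.962 = 2.67 mm

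Coverage is the probability that the interval contains the true change when its centre is shifted by b. It equals one minus the two-sided noncentral-t rejection probability with noncentrality b√n / 2.15.

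| | b = 0.25 | b = 0.5 | b = 1.0 |
|---|---|---|---|
| b / 4.36 | 5.7% | 11.5% | 22.9% |
| b / half-width, n = 8 | 13.9% | 27.8% | 55.6% |
| b / half-width, n = 5 | 9.4% | 18.7% | 37.5% |
| Coverage, n = 8 | 0.941 | 0.912 | 0.793 |
| Coverage, n = 5 | 0.945 | 0.931 | 0.872 |
| Rejecting zero at true 4.36 mm, n = 8 (0.9980 unbiased) | 0.9992 | 0.9997 | 1.0000 |
| Rejecting zero at true 4.36 mm, n = 5 (0.9157 unbiased) | 0.9399 | 0.9582 | 0.9813 |

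**Step 4: rate and secondary outcomes**

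If 4.36 mm takes the full eight months named in the research question, the rate is 4.36 / 8 = 0.545 mm per month. The bias adds b / 8 = 0.031, 0.063 or 0.125 mm per month, in the same proportions as for the amount. For a secondary change of 1 mm (an assumption), the same bias is 25% to 100% of the change.

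**The case against.** The strongest reply is that masking can achieve little here. A shift of about 4 mm, a narrowing second-molar space or visible mini-implants may show the time point, and a treating investigator may recognise cases in a sample of about eight. This largely stands for the start-to-end comparison, and it is why the protocol should call the masking partial. It has less force for casts taken four weeks apart, where the expected movement is about half a millimetre on the eight-month assumption, and for small secondary changes.

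A second reply is that the size of the bias is assumed. That is correct. The fall in coverage to 79% occurs only at 1.0 mm; at 0.25 mm the loss is about one percentage point or less. The percentages for rate repeat those for amount and are not separate evidence. The protocol also does not say how rate will be calculated, so reliance on the visit-by-visit models is an inference.

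Third, being responsible for extraction does not exclude other people doing the reading, and the protocol never says that the principal investigator is the unblinded operator. The two passages are therefore unclear rather than contradictory. They still need to say who measures.

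Fourth, coded IDs arguably hide the name on casts as well. That is so, but they are not said to hide the visit.

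Finally, if the measurements used superimposition, records would have to be read in pairs. The protocol does not adopt that method, and its example cast measure (upper molar cusp to lower molar groove) can be read on a single record.

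**Conclusion.** The concern holds. Followed exactly, the Blinding paragraph leaves the time point visible, does not cover the scanned casts and does not settle who reads the records. This follows from the text and needs no assumption.

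The consequence is a risk of bias in the estimated amount and rate of distalization and in small secondary changes. For an assumed directional bias of 0.25 to 1.0 mm, that is 6% to 23% of the planned change, or 14% to 56% of the interval half-width at n = 8. The rejection of zero change is practically untouched at n = 8. This is a weakness that should be corrected in the only blinding safeguard of an uncontrolled study; it does not invalidate the design or the sample size.

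**What to change.** Replace the assessor sentence in the Blinding paragraph with text such as: *Every CBCT volume and every scanned cast (pre, follow-up and post) is stripped of name, date and visit and given a random code by a supervisor or the statistician. Study measurements are made in random order after the last patient finishes, and the code is broken only after the measurements are locked.*

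State who measures, preferably a team member who did not treat the patients. If it is the investigator, say so. Bring the Statistical analysis paragraph in section VII into line. Add that masking is partial, because tooth position, mini-implants still in place or recognition of a case may reveal the time point, and do not describe the assessment as fully blinded.

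The cost is renaming files, moving the study measurements to the end, and some reading time if a non-treating team member is used. Treatment, visits and sample size do not change. The gain is real but limited, for the reasons that make the masking partial.
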